4.3.1.2. Analysis using MMRM Method for the PP Population

The analysis of the primary endpoint using MMRM method will also be conducted for the Per Protocol (PP) population (defined in Section 2.1).

4.3.1.3. Sensitivity Analyses

Sensitivity analyses will be conducted using the following methods to assess the impact of missing data and the robustness of the primary analysis.

Multiple Imputation/ANCOVA Method

Multiple Imputation is a broadly applicable technique for handling missing data. Missing data are imputed multiple times using a regression method. Each imputed data set is analyzed by analysis of covariance (ANCOVA) model, and the point estimates and standard errors are combined to provide inferences that reflect the uncertainty about the missing values. MI also makes assumption of missing at random (MAR) mechanism.

Primary endpoint data that are missing will be multiply imputed separately for each treatment arm using a regression procedure, with baseline information including baseline score, genotype, age at ATTR onset, prior tetramer stabilizer use, region, KPS, FAP stage (I vs. II/III), cardiac subpopulation and gender, as well as 9-month efficacy assessment value (when available) as covariates. MI assumes monotone missingness. For non-monotone missing data, e.g., patients completely missing the 9-month assessment but for whom the 18-month assessment is available, the 9-month assessment will be imputed as the treatment group mean. The proportion of non-monotone missing data is expected to be very small.

After imputation, the complete dataset will be analyzed using the ANCOVA model. In the model, baseline mNIS+7 will be used as covariate and treatment arm (patisiran vs. placebo), genotype (V30M vs. non-V30M), age at ATTR onset (Before age 50 vs. After age 50), prior tetramer stabilizer use (Yes vs. No), and region (Western EU, North America, and Rest of World) as factors.

One hundred imputed datasets (per treatment arm) will be generated from the MI regression procedure. Each of the imputed datasets will then be analyzed via the ANCOVA model and the resulting estimates (LS means and standard errors) combined using SAS PROC MIANALYZE to produce inferential results (difference in LS means, 95% CI for the difference, and the p-value from the test that the difference is zero). Point estimates (LS means and differences) will be calculated as the average of the 100 complete-data estimates. A total variance estimate will be calculated as a weighted sum of within-imputation variance, which is the average of the complete-data variance estimates, and a between-imputation variance term. Complete details may be found in the SAS documentation for the MIANALYZE procedure (see Combining Inferences from Imputed Data Sets under Details).

<http://support.sas.com/documentation/onlinedoc/stat/131/mianalyze.pdf>.

Analyses will be conducted using PROC MI and PROC MIANALYZE in SAS 9.3 (or later).

Pattern-Mixture Model (PMM)

A sensitivity analysis using pattern mixture model (PMM) will be performed to assess the robustness of the primary MMRM results to the possible violation of the missing at random (MAR) missingness assumption. The PMM accommodates situations where the missingness mechanism is missing not at random (MNAR). The model will be based on the following assumptions:

1. Patients who have missing data and are alive before Month 18:
 - a. Placebo patients who have missing data (either Month 9 or 18): The missing data are considered MAR and will be imputed using MI estimated from placebo patients. The imputation is done regardless of whether a patient was on-treatment or discontinued treatment before the scheduled efficacy assessment.
 - b. Patrisiran patients who have missing data (either Month 9 or 18) while on treatment: Patients are expected to continue to show benefit from treatment

similar to that observed at the scheduled time point. Therefore, missing data during the on-treatment period (within 60 days of their last dose) are considered MAR and will be imputed using MI estimated from all non-missing data collected on treatment from the patisiran arm.

- c. Patisiran patients who have missing data (either Month 9 or 18) after stopping their study treatment: Patients will no longer benefit from treatment in the future and will have trajectory similar to placebo patients. Therefore, missing data after treatment discontinuation (more than 60 days after last dose of study drug) will be imputed using the data from placebo patients.
2. Patients who die before Month 18 and have missing data: Assuming that deaths observed in the study will likely be related to worsening of disease, the missing data at Month 18 will be imputed by taking random samples from the worst 10% mNIS+7 change scores in the entire population. The imputation will be done for patients from both patisiran and placebo arms.

Missing values will be imputed 100 times to generate 100 complete datasets using procedures as described above. An ANCOVA model will be fit to each “complete” dataset for the change from baseline in mNIS+7 at Month 18. The ANCOVA model will include baseline mNIS+7 as a continuous covariate and treatment arm (patisiran vs. placebo), genotype (V30M vs. non-V30M), age at ATTR onset (Before age 50 vs. After age 50), previous tetramer stabilizer use (Yes vs. No), and region (Western Europe, North America, and Rest of World) as factors. The resulting estimates from the 100 analyses will be combined using Rubin’s formulae, and the 95% confidence interval will be constructed, similar to the procedure described in the MI/ANCOVA section.

More details on the implementation of PMM are discussed in Appendix 7.1.

Including Data Post Alternative Treatment for FAP

The primary analysis will not include mNIS+7 assessments performed after the initiation of alternative treatment for FAP (Section 3.7). Sensitivity analysis including data post alternative treatment for FAP will be conducted using the MMRM model. In this sensitivity analysis, all assessments will be used in the analysis regardless of whether an assessment occurs before or after alternative treatment.

Revised mNIS+7 Total Score Using a Different Algorithm to Handle Missing Components

In the primary derivation of mNIS+7 total score, the “within treatment arm” imputation algorithm will be used for the imputation of missing component (Appendix 7.2.1). At each visit, if a patient has a missing component for mNIS+7, the value will be imputed using data from other patients who are on the same treatment arm and who had non-missing data for that component at that visit. In a sensitivity analysis, any such missing value will be imputed as the mean value for the component at the visit from all patients (combining placebo and patisiran arms). The analysis of this revised mNIS+7 derived scores will be conducted using the MMRM model.

4.3.1.4. Binary Analyses

The number and percentage of patients with < 10-point increase in mNIS+7 composite score from baseline to Month 18 will be calculated for each treatment arm and compared between 2 arms using the Cochran-Mantel-Haenszel test, stratified by genotype (V30M vs. non-V30M). The percentage will be based on the mITT population. Patients with missing 18-month data will be counted in the denominators.

In addition, the number of percentage of patients with a decrease (change from baseline < 0-point) in mNIS+7 total score from baseline to Month 18 will also be calculated and analyzed similar as above.

The planned analyses of the primary endpoint mNIS+7 are summarized in [Table 1](#).

Table 1 Analysis of mNIS+7

Statistical Method	Analysis Population
Primary analysis: MMRM	mITT
Sensitivity analysis: 
 • MI/ANCOVA • PMM • MMRM - including Data Post Alternative Treatment for FAP • MMRM - revised mNIS+7 Total Score Using a Different Algorithm to Handle Missing Components 	mITT
Other analysis: MMRM	PP
Other analysis: Binary analysis using stratified CMH	mITT

4.3.2. Secondary Efficacy Evaluations

Secondary efficacy endpoints include Norfolk QOL-DN total score, NIS-W, R-ODS, 10-meter walk test speed, mBMI, and COMPASS-31. To control overall type I error, these endpoints will be tested in a hierarchical order as described in Section 3.6.

All the secondary endpoints are assessed at baseline, Month 9, and Month 18 with the exception of mBMI. mBMI is assessed at baseline, Day 84, Day 189, Day 357, Day 462 and Day 546. Day 546 will be used as Month 18 assessment.

For 10-meter walk test, the walk speed for patients unable to perform the walk will be imputed as 0. The change from baseline will then be calculated as 0 – baseline walk speed.

Change from baseline at Month 18 in the secondary efficacy endpoints will be analyzed for the mITT population, using an MMRM model similar to the model described for the primary analysis of mNIS+7 while adjusting for baseline value of the endpoint being modeled. For these secondary endpoints (except NIS-W), MMRM model will also include baseline NIS (< 50 vs. ≥ 50) as a factor. The MMRM model for NIS-W will not include baseline NIS since baseline NIS-W will be included as a covariate in the model.

For the first secondary endpoint Norfolk QOL-DN Total Score, the MMRM method will also be conducted for the PP population. In addition, sensitivity analyses will be conducted using ANCOVA/MI and including data post alternative treatment for FAP similar as described for mNIS+7 (see Section 4.3.1.3).

Month 18 change from baseline in mBMI will be estimated from the MMRM model using assessment results from all time points.

The planned analyses of the secondary endpoints are summarized in [Table 2](#).

Table 2 Analysis of Secondary Endpoints

Endpoint	Statistical Method	Analysis Population	Special Notes
Norfolk QOL-DN total score	Primary analysis: MMRM	mITT	
	Sensitivity analysis: 
 • MI/ANCOVA • MMRM - including Data Post Alternative Treatment for FAP 	mITT	
	Other analysis: MMRM	PP	
NIS-W	MMRM	mITT	Excludes data post alternative treatment for FAP
R-ODS	MMRM	mITT	
10-meter walk test speed	MMRM	mITT	For patients unable to perform the walk, walk speed imputed as 0
mBMI	MMRM	mITT	Measured at baseline, Day 84, Day 189, Day 357, Day 462 and Day 546
COMPASS-31	MMRM	mITT	

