
Other Assessments
	
Disease burden and healthcare utilization will be assessed using a patient-reported pharmacoeconomics questionnaire. The investigator will periodically assess mental status as it relates to suicidal ideation and behavior by using the Columbia–Suicide Severity Rating Scale (C-SSRS) questionnaire.

Follow-Up
	
Patients who complete the 18-month efficacy assessments can elect to participate in an extension study in which patients would receive open-label administration of 0.3 mg/kg patisiran once every 21 days. Eligible patients who elect to participate will return for a follow-up visit 21 days after last dose of study drug.
 
If the patient decides not to participate in the extension study, the patient will complete 2 follow-up visits at 21 and 56 days after the last dose of study drug. Each follow-up visit includes safety assessments and the 21-day follow-up also includes PD measurements.

Statistical Methods
	
A full statistical analysis plan (SAP) will be finalized prior to database lock.
 
The primary analysis will compare patients administered patisiran versus those administered placebo in the modified intent-to-treat (mITT) population. Specifically, patients who are randomized and receive at least 1 dose of study drug will be included in this analysis. The primary analysis will compare change in mNIS+7 from baseline at 18 months between patisiran and placebo groups, adjusted for the stratification factors. Analysis of covariance (ANCOVA) will be used to analyze the primary endpoint. Primary endpoint data that are missing will be inferred using multiple imputations. Sensitivity analyses, including mixed model repeated measures (MMRM) analyses, will assess the robustness of the primary analysis for the mITT and per protocol (PP) populations.
 
Type I error control for secondary endpoints will be achieved by a hierarchical ordering procedure. Briefly, endpoints will be evaluated in order to control for multiplicity.
 
An independent interim analysis committee (IAC) will conduct a blinded interim analysis when approximately 50% of patients have completed their 9-month mNIS+7 assessments. This

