9.2.3.2 Secondary Efficacy Endpoints

Secondary efficacy endpoints will be analyzed using methods similar to those employed for the primary analysis, e.g. ANCOVA with multiple imputations, as appropriate.

Type I error control for secondary endpoints will be achieved by a hierarchical ordering procedure. Endpoints will be tested in the following prespecified hierarchy:

- Norfolk QOL-DN questionnaire;
- NIS-W score;
- mBMI;
- Timed 10-meter walk test;
- COMPASS-31.

If and only if a comparison is significant at $p < 0.05$, the next endpoint in the hierarchy may be tested.

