3.2. General Methods

All data listings that contain an evaluation date will contain a study day relative to the day of the first dose of study drug, which is designated as Day 1. On-treatment study days will be calculated as evaluation date – first dose date +1 and pre-treatment days will be calculated as evaluation date – first dose date. For example, the day prior to study drug administration will be Day -1, the first dose day of study drug will be Day 1 and the day after the first dose of study drug will be Day 2, etc.

All output will be incorporated into Microsoft Word files, sorted and labeled according to the International Conference on Harmonisation (ICH) recommendations, and formatted to the appropriate page size(s).

For categorical variables, summary tabulations of the number and percentage of patients within each category (with a category for missing data) of the parameter will be presented. For continuous variables, the number of patients, mean, median, standard deviation (SD), minimum, and maximum values will be presented.

Laboratory data (including vitamin A and RBP) collected and recorded as below the limit of detection will be set equal to the lower limit of detection for the calculation of summary statistics.

For assessments that are repeated multiple times on the study day (e.g., 10-meter walk tests, IENFD, SGNFD, etc.), the average will be calculated unless otherwise noted.

Formal statistical hypothesis testing will be performed on the primary and secondary efficacy endpoints with all tests conducted at the nominal 2-sided 0.05 level of significance. Secondary endpoints will be tested in a prespecified hierarchy (Section 3.6). Summary statistics will be presented, as well as 2-sided 95% confidence intervals on selected parameters, as described in the sections below.

All summaries will be presented by treatment arm. All data recorded on the CRF will be included in data listings.

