3.6. Multiple Comparisons/Multiplicity

Type I error control for secondary endpoints will be achieved by a hierarchical ordering procedure. Endpoints will be tested in the following pre-specified hierarchy:

1. Norfolk QOL-DN questionnaire [Total Score]
2. NIS-W score

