3. R-ODS
4. 10-meter walk test speed
5. mBMI
6. COMPASS-31 total score

Only if a comparison is significant at a 2-sided 0.05 significance level, the next endpoint in the hierarchy may be formally tested; if a given comparison is not significant at a 2-sided 0.05 significance level, the subsequent tests will be performed and the results summarized, but statistical significance will not be inferred.

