4.3.1.1. Primary Analysis using MMRM Method for the mITT Population

The primary analysis will be performed using a restricted maximum likelihood (REML) based MMRM approach. The outcome variable is change from baseline in mNIS+7. The model includes baseline mNIS+7 score as a continuous covariate and fixed effect terms including treatment arm, visit (Month 9 or Month 18), treatment-by-visit interaction, genotype (V30M vs. non-V30M), age at hATTR Symptom onset (< 50 ; ≥ 50), region (North America, Western Europe, and Rest of World), and previous tetramer stabilizer use (yes vs. no). An unstructured covariance structure will be used to model the within-patient errors. The Satterthwaite approximation will be used to estimate the degrees of freedom. The primary comparison is the contrast (difference in least squares means [LS means]) between the patisiran and placebo groups at 18 months. Analysis will be implemented with SAS PROC MIXED.

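### The secondary hierarchy starts at Norfolk QOL-DN without requiring a significant mNIS+7 result, so as written it controls error among the secondaries only, not across primary and secondaries

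*SAP*

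**What the plan says.** SAP 3.6 sets the scope: "Type I error control for secondary endpoints will be achieved by a hierarchical ordering procedure". Its list runs Norfolk QOL-DN, NIS-W, R-ODS, 10-meter walk speed, mBMI, COMPASS-31. The rule for moving down it is "Only if a comparison is significant at a 2-sided 0.05 significance level, the next endpoint in the hierarchy may be formally tested". If a listed endpoint fails, later ones are still run and summarized, but no significance is inferred. Nothing comes before Norfolk QOL-DN, and nothing is said about what happens if mNIS+7 fails.

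SAP 3.2 covers both levels: "Formal statistical hypothesis testing will be performed on the primary and secondary efficacy endpoints with all tests conducted at the nominal 2-sided 0.05 level". It then adds "Secondary endpoints will be tested in a prespecified hierarchy", which leaves the primary outside the ordering. SAP 4.3.1.1 defines the primary test ("The primary comparison is the contrast (difference in least squares means [LS means]) between the patisiran and placebo groups at 18 months") and does not connect it to the secondaries.

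SAP 4.3.2 gives the purpose of the ordering: "To control overall type I error, these endpoints will be tested in a hierarchical order as described in Section 3.6". SAP 5.3, recounting the order in the protocol and SAP V1.0, attributes the same overall aim to it. Section 5 is printed twice in the SAP file.

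Protocol 9.2.3.2 has the same structure. Its list also begins at Norfolk QOL-DN, and significance on one listed endpoint means that "the next endpoint in the hierarchy may be tested". The protocol synopsis says only "Briefly, endpoints will be evaluated in order to control for multiplicity". Protocol 9.2.3.1 says when efficacy is established: mNIS+7 must improve relative to placebo with a 2-sided p-value of at most 0.05. It does not make this a condition for secondary testing.

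**The concern.** A fixed sequence protects the error rate of the endpoints that stand in it. mNIS+7 does not stand in this one. The primary has its own 0.05 and the secondary sequence opens with another 0.05, with no link between them. A rule of that shape does not deliver error control over the primary and secondaries together, which is the natural reading of 'overall' in SAP 4.3.2.

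The case at stake is a missed primary. Read literally, the plan then still allows Norfolk QOL-DN to be formally tested and called significant, followed by NIS-W and the rest. Whether such results count as confirmatory or as descriptive could then be open to dispute once the data are known, and a multiplicity rule exists to prevent that.

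**Working it through.** **1. The plan's own figures.** No familywise figure is stated, so there is none to reproduce. A level of 5% 2-sided, or 2.5% for a false claim of benefit, is inferred from the per-test level in SAP 3.2. As background, the sample size reproduces from SAP 3.1 (difference 8.95, SD 16, 90% power, 2-sided 0.05) with 2:1 allocation. Placebo n = 1.5 × 16² × (1.960 + 1.282)² / 8.95² = 50.4, rounded up to 51. With 102 on patisiran the total is 153, against 154 stated. Nothing below changes it.

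**2. Where a condition on mNIS+7 could stand.**

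| Place | What it links |
|---|---|
| SAP 3.2 | Levels only; the hierarchy covers secondaries |
| SAP 3.6 | Each listed secondary to the next; starts at Norfolk QOL-DN |
| SAP 4.3.1.1 | Defines the primary contrast only |
| SAP 4.3.2 | Refers back to 3.6 |
| Protocol 9.2.3.1 | Established efficacy to mNIS+7 only |
| Protocol 9.2.3.2 | As SAP 3.6 |
| Protocol synopsis | Ordering in general terms; no endpoint named first |

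None of them makes mNIS+7 a condition for Norfolk QOL-DN.

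**3. Neither mNIS+7 nor Norfolk QOL-DN has an effect.** Each test gives a false claim of benefit with probability 0.025 (Z > 1.96). Let ρ be the correlation of the two test statistics and J(ρ) the probability that both exceed 1.96 (bivariate normal). Then:

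- As written: P(false benefit on either) = 0.025 + 0.025 − J(ρ).
- With a primary-first condition that names the direction: 0.025 at every ρ, because nothing can be claimed unless mNIS+7 is.

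| ρ (assumed) | J(ρ) | As written | With condition | Excess |
|---|---|---|---|---|
| 0 | 0.0006 | 0.0494 | 0.0250 | 0.0244 |
| 0.5 | 0.0046 | 0.0454 | 0.0250 | 0.0204 |
| 0.7 | 0.0083 | 0.0417 | 0.0250 | 0.0167 |
| 0.9 | 0.0148 | 0.0352 | 0.0250 | 0.0102 |

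A simulation with 4,000,000 draws agrees: 0.0492, 0.0454, 0.0419 and 0.0353. The documents give no value of ρ. Zero is unlikely, since protocol 7.2.1 and 7.2.9 describe both instruments as covering small fiber, large fiber and autonomic function.

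**4. Norfolk QOL-DN truly works; mNIS+7 and NIS-W do not.** Norfolk then usually passes and opens NIS-W. Assume 90% power for Norfolk QOL-DN. NIS-W supplies 192 of the 304 mNIS+7 points (protocol Appendix 4; SAP 7.2.1), or 192/304 = 63%, so the two statistics must be strongly correlated; 0.8 to 0.95 is assumed. If Norfolk is uncorrelated with both, the chance of a false benefit claim on mNIS+7 or NIS-W is 0.025 + 0.90 × [0.025 − J]:

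- Correlation 0.8: 0.025 + 0.90 × 0.0140 = 0.0376.
- Correlation 0.9: 0.025 + 0.90 × 0.0102 = 0.0342.

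Letting Norfolk correlate with both at up to 0.7 (simulation, 4,000,000 draws) gives about 3.8% to 3.9% at 0.8, 3.4% to 3.5% at 0.9 and 3.2% at 0.95. With the condition the figure is 2.5%.

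**5. mNIS+7 has a true effect.** A false claim can then arise only among the secondaries, where the sequence already works. With Norfolk QOL-DN null and mNIS+7 at 90% power, the false Norfolk benefit claim is 2.5% as written and 2.25% to 2.5% with the condition. The existing text causes no excess.

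**The case against.** The strongest reply is that nothing here contradicts itself. SAP 3.6 and protocol 9.2.3.2 confine the procedure to the secondary endpoints, and within that family it does control error. SAP 3.2 calls its 0.05 nominal, which describes a per-test level. If 'overall' in SAP 4.3.2 means over the secondary family, the sentence is true. This stands: the defect is a missing sentence, and a reader who concludes that the plan makes a false statement goes further than the text allows.

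It can also be said that testing the primary first is the convention and was surely meant. It probably was. But SAP 3.6 says what follows when a secondary fails and is silent on what follows when the primary fails, so the convention would have to be read in at the one point where it matters.

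A reader might infer that a failed trial could be declared a success on Norfolk QOL-DN. The documents do not support that. Protocol 9.2.3.1 ties established efficacy to mNIS+7 alone, with a direction. What stays open is narrower: whether a secondary may be called significant after mNIS+7 misses.

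A reader might also infer that the error rate nearly doubles, to 1 − 0.95² = 9.75%. That figure counts false findings of harm and needs uncorrelated endpoints. Likewise, step 4 run with zero correlation gives 4.7%, but that treats NIS-W as unrelated to a score of which it is the largest part.

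**Conclusion.** The point holds as a gap in pre-specification. The rule as written controls error within the secondary family and not over the primary plus the secondaries, while SAP 4.3.2 and 5.3 speak of overall control. For a false benefit claim on mNIS+7 or Norfolk QOL-DN when both are null, the excess over 2.5% is 1.0 to 2.4 percentage points for assumed correlations of 0.9 down to 0, with the upper end unlikely. When Norfolk QOL-DN works but mNIS+7 and NIS-W do not, the excess is about 0.7 to 1.4 points (3.2% to 3.9% against 2.5%), assuming 90% power for Norfolk QOL-DN and an mNIS+7/NIS-W correlation of 0.95 to 0.8. There is no excess if mNIS+7 has a true effect. The primary test and the criterion for established efficacy are untouched. It should be fixed before unblinding because the repair is small and the question arises only after a missed primary.

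**What to change.** Add to SAP 3.6, with a cross-reference in 4.3.2:

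> Norfolk QOL-DN will be formally tested only if the primary comparison (mNIS+7, MMRM, Month 18, mITT) is significant at the 2-sided 0.05 level in favor of patisiran; otherwise all secondary results will be summarized without inferring statistical significance.

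Record it in SAP section 5 as a clarification of protocol 9.2.3.2. Naming the direction is a refinement: without it the false-benefit rate in step 3 would be 0.0256 at ρ = 0 and 0.0250 from ρ = 0.5. The sentence should also settle one convention for the boundary, since protocol 9.2.3.1 allows p equal to 0.05 and 9.2.3.2 does not.

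If the sponsor means to protect the secondary family only, replace the reference to overall type I error in SAP 4.3.2 and in both printings of 5.3 with the narrower scope already used in SAP 3.6.

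The added sentence leaves the primary test, its alpha, its power and the sample size unchanged. Its price is that no secondary can be formally claimed if the primary fails. At the design's 90% power that would happen in 1 − 0.90 = 10% of trials even if the planned mNIS+7 effect is real.
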